#### 2. Background and rationale

#### 2.1. What is the problem being addressed?

Having the **right number of nurses** caring for patients on hospital wards is vital for patient safety but planning for varying numbers of patients with unknown deterioration/recovery trajectories is hard.(1, 2) Extensive research shows that care quality and safety are compromised when nurse staffing is low,(3-6) but deciding how to allocate nursing staff is challenging because demand for care fluctuates;(7) both patient numbers and their needs vary over time. Decisions arise at multiple points including determining how many staff to employ (the establishment) and how many to deploy on each shift.(8) Given current staffing shortages, being able to identify wards to prioritise and (potentially) identify any spare staffing capacity is especially important.

To help guide decisions, a range of **tools attempt to measure demand** for nursing care and determine the required number of staff.(9) In England, the NICE-endorsed Safer Nursing Care Tool (SNCT), now used in almost all acute NHS Trusts.(10) Designed for establishment planning, it requires that patients are classified into one of five categories based on an assessment of acuity and dependency on nursing care. The category 'multipliers' reflect the relative demand for care and formulae are provided to estimate the number of nurses to employ to safely staff the ward, allowing for variation in demand and staff absences. When used for establishment planning, trained nurse observers assess all patients on a ward daily for 30 days and the establishment is set based on an average.(11) Increasingly the acuity/dependency classification is carried out by clinical nurses, sometimes multiple times per day, and results are used for real-time monitoring of demand and to guide deployment of staff.(7, 12)

However, the SNCT approach is **labour-intensive** and necessitates the collection of data specifically to measure staffing requirements, not informed by data gathered for administration or care management. Because SNCT assessments are intermittent, there is limited ability to monitor demand and take actions to match it in real-time. Even when used for establishment setting, prescribed methods for sampling do not reflect typical demand on some types of ward.(7, 13) Furthermore, the use of a limited number of categories does not reflect the continuous variability of need.

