But in order to make decisions about redeploying staff or hiring temporary staff, **accurate information** about ward staffing requirements needs to be available in a **timely** way, which is currently not the case across the NHS. Providing up-to-date, objective and accurate information about demand for nursing care has large potential benefits, allowing areas at risk of short-staffing to be identified and prioritised for the deployment of staff.(8) Trusts are already using software for deployment decisions (generally using an acuity dependency measure based on the SNCT), which demonstrates this is seen as necessary, but the SNCT was neither designed nor validated for this purpose.

Currently the NHS faces significant and enduring **staff shortages**,(14) making it especially important to deploy the available staff efficiently and effectively. Reducing cases of severe or sustained understaffing on a ward has potential benefits for staff as well as the organisation more generally; prolonged exposure to understaffing is a risk factor for staff burnout as well as staff turnover and sickness absence.(18, NIHR 128056 under review)

Additional **benefits of workforce planning tools** and technologies include promoting the patient safety agenda within a Trust and helping learn 'what works' in effective staffing by comparison across wards.(19) Although there are problems with the translation from research to practice,(1) there is evidence that when a user-centred design approach is used, tools can be successfully designed and implemented by embedding in existing software.(20)

Minimising the **administrative burden** on staff of gathering data to monitor staffing requirements is also important. While assessing an individual patient to determine the SNCT category is not unduly time-consuming, when multiplied across patients and multiple daily assessments (as is increasingly being done), the workload is considerable. Our observational data (unpublished) suggests that assessing all patients on a thirty-bedded ward three times per day could occupy a senior nurse for up to 30 minutes per day, plus extra time for data entry. Additionally, to ensure reliable and accurate assessments, considerable time is required to train and assess staff competence, with high staff turnover and reliance on temporary staff creating further challenges.

Ethics/ERGO no: 100780; IRAS no: 346148

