#### 2.3. Review of existing evidence

There is a clear continued demand for nurse workforce planning tools and systems to help with nurse staffing decisions, as demonstrated by the large volume of papers on tool development, dating back to the 1920s and still proliferating today.(9, 21) These tools include volume-based methods (such as patient-to-nurse ratios), patient prototype/ classification, professional judgement and timed-task approaches. Multiple review papers have found that despite the continual development of new tools, there is little evidence for their effectiveness in recommending appropriate staffing levels, as most papers focus on tool development rather than validation.(9, 22-24) In a survey with responses from 91 of the 148 acute care Trusts in England, 80% reported using the SNCT alongside their professional judgement for establishment reviews.(10) They also reported reviewing the adequacy of nurse staffing at the start of each shift with 75% of Trusts using professional judgement and 69% of Trusts using patient acuity/dependency systems.(10) A previous HS&DR-funded ethnographic study also found evidence for the usefulness of tools, with identified "programme theories" including that NHS managers need to combine local knowledge and professional judgement with data from workforce planning and deployment tools and technologies for effective staffing decisions.(19)

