#### 4.4.1. Data sources

The **data sources** are a range of hospital systems which will differ by Trust. The Safer Nursing Care Tool data that is collected twice-yearly for establishment reviews will be sourced from the relevant spreadsheets/Trust records, and where available the SNCT data that is recorded for deployment decisions will be extracted from the electronic roster (RLDatix SafeCare system). Patient data will be sourced from various IT systems storing patient administration records, nursing care documentation, care plans, pharmacy and surgery records. We will supplement this with contextual information about wards sourced directly from our Trust nursing contacts.

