## 4.5. Workstream 3: Validating measures of nurse staffing requirements against patient outcomes and nurse perceptions of inadequate staffing

We will conduct a retrospective observational study to investigate the associations between actual under/over-staffing relative to each candidate measure of staffing requirements and a range of outcomes. One would expect that as staffing increases relative to a measure, the risk of poor patient outcomes and perceptions that staffing is inadequate decreases.(13, 26) In the absence of a gold standard, we will compare model fit against models with staffing requirements measured by the SNCT, as well as against the current ward establishments where possible. For this we will use routine data extracted from hospital IT systems along with an empirical (prospective) micro-survey of nurses (three tick-boxes) to understand perceptions of staffing adequacy.

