#### 4.5.2. Variables

We will consider a range of **patient outcome variables**. Our primary patient outcome is mortality within 30 days of admission, as it has a strong association with staffing levels.(5, 17) Other patient outcomes we will model include length of stay, readmissions within 30 days (which both have high strength of evidence for an association with staffing levels according to a recent review)(4) and healthcare-associated conditions such as pneumonia and pressure ulcers (which have moderate evidence).(4) We will limit the latter analyses to surgical patients since for medical patients it is harder to distinguish between complications and conditions present on admission.

Our other outcomes are measures of **perceived staffing adequacy** assessed through the prospective micro-survey. We will ask clinical nurses three questions as in our previous study: i) Were there enough staff for quality?, ii) Were breaks missed? and iii)Was care left undone?(13) These were derived following pilot work of a more extensive set of questions, and are aimed to be quick to answer and give a good indication of overall staffing adequacy on a ward. In our previous study these were all associated with deviation from SNCT-recommended staffing.(13)

Ethics/ERGO no: 100780; IRAS no: 346148

Our **independent variables** are the deviation of actual staffing from measures of staffing required. In other words, under-/over-staffing compared to different measures of what is needed. Actual (achieved) staffing is measured as total care hours per patient day and includes all nursing staff on the ward: both Registered Nurses and Support Workers, both permanent and temporary (bank or agency) staff. Required staffing will be measured in different ways including: using the SNCT, current ward establishments, algorithmic measures (including the ward-level and patient-level approaches).

To start with we will model overall staffing but where possible will also consider **skill mix** by splitting out staff groups. We will use current ward establishments to calculate the planned skill mix and apply these to our alternative measures of staffing requirements. This will allow us, for example, to assess Registered Nurse understaffing and Support Worker understaffing separately, which is important since differing relationships have been found with patient outcomes.(5) We will use the pay band to categorise staff, given the differences in roles and job titles between Trusts.

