We will compare how well different measures of staffing requirements appear to capture workload according to Akaike Information Criterion **model fit.** We will also compare the benefits of using alternative staffing requirement measures by using decision analytic methods like **decision analytic curves**, as deployed in research about the Rafaela staffing tool.(26) The advantage of this method is that it provides an estimate of net benefit without requiring additional data on costs or quality-adjusted life years.(53)

Ethics/ERGO no: 100780; IRAS no: 346148

We will investigate the impact of changing our modelling approach and assumptions through **sensitivity analyses**, for example varying the exposure window and fitting alternative model types. We will also run subgroup analyses to understand the fit for particular patient groups.

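### Where SNCT scores guide shift deployment, the AIC ranking of separate deviation models cannot be read as a ranking of how well SNCT and the algorithm measure need

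*Protocol*

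**What the plan says.** Protocol section 4.5 makes SNCT the main comparator: "In the absence of a gold standard", the text runs, "we will compare model fit against models with staffing requirements measured by the SNCT"; current ward establishments are a further comparator where possible. Section 4.5.2 defines the exposures, which "are the deviation of actual staffing from measures of staffing required". Section 4.5.3 gives the criterion: "We will compare how well different measures of staffing requirements appear to capture workload according to Akaike Information Criterion".

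The same protocol describes how actual staffing comes about. Section 2.1 says of SNCT classification that "results are used for real-time monitoring of demand and to guide deployment of staff". Section 2.2 says "Trusts are already using software for deployment decisions (generally using an acuity dependency measure based on the SNCT" (the bracket closes shortly after). Section 2.3 reports, for staffing reviews at the start of each shift, "69% of Trusts using patient acuity/dependency systems". Section 4.4.1 makes those scores study data: "where available the SNCT data that is recorded for deployment decisions will be extracted from the electronic roster".

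The sensitivity analyses named in section 4.5.3 are examples (exposure window, model type). None deals with staffing having been set from one of the measures under comparison.

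**The concern.** Ranking deviation models by fit is a fair test of two requirement measures only if neither helped to determine actual staffing. SNCT did, to an unstated degree. Suppose SNCT overstates need on a ward and staff are moved there. The ward is then truly overstaffed, yet its SNCT deviation is near zero. The deviation from an algorithm nobody acted on still shows the surplus. The algorithm therefore tracks outcomes better because SNCT was used, not because SNCT measured need worse.

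At stake is the interpretation of the comparison. Section 5 makes correspondence with patient and staffing-adequacy outcomes one of the conditions for taking the algorithms further. A fit advantage could be taken as evidence of better measurement when part of it comes from past use of the comparator.

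**Working it through.** **The plan's own figures.** The protocol gives no figure for the fit comparison, only the ward-days available (Sample sizes, under 4.5). Lower: 30 × 2 × 20 = 1,200 per Trust, × 5 = 6,000. Upper: 0.85 × 273.75 days × 20 = 4,653.75, stated as 4653, and 4,653 × 5 = 23,265. Both reproduce.

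**Set-up.** True need T, variance 1. SNCT = T + e1 and algorithm = T + e2, each error with variance 0.5 (equal accuracy) and correlation ρ. Staffing S = b·SNCT + u, variance of u 0.5, where b is how far staffing responds to SNCT. The outcome signal is S − T. All variances, b and ρ are assumptions, because the documents give none.

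- S − T = (b−1)T + b·e1 + u
- S − SNCT = (b−1)T + (b−1)e1 + u
- S − algorithm = (b−1)T + b·e1 − e2 + u

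The share of signal explained is R² = cov² / (product of variances).

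**b = 0.5.** Var(S − T) = 0.25 + 0.125 + 0.5 = 0.875.
- SNCT: variance 0.875, covariance 0.25 − 0.125 + 0.5 = 0.625. R² = 0.625² / 0.875² = 0.51.
- Algorithm: variance 1.375 − 0.5ρ, covariance 0.875 − 0.25ρ.
  - ρ = 0: 0.875² / (0.875 × 1.375) = 0.64
  - ρ = 0.5: 0.75² / (0.875 × 1.125) = 0.57
  - ρ = 0.8: 0.675² / (0.875 × 0.975) = 0.53

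**Other values of b, ρ = 0.**

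| b | SNCT | Algorithm |
|---|---|---|
| 0 | 0.75 | 0.75 |
| 0.3 | 0.61 | 0.67 |
| 0.5 | 0.51 | 0.64 |
| 1 | 0.50 | 0.67 |

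**General result at b = 1.** Write su for the variance of u, se for the error variance and d = se(1 − ρ). SNCT's R² is su/(su+se). The algorithm's is (su+d)² / [(su+se)(su+2d)]. The algorithm is higher whenever ρ < 1, since (su+d)² − su(su+2d) = d² > 0. Over a grid of 7,200 settings with b > 0 and equal accuracy, SNCT fitted better in 177. Those inspected were settings where the SNCT slope takes the wrong sign.

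**AIC at the plan's sample sizes.** A logistic simulation with the same staffing equation (60 replicates per setting; its parameters are also assumptions) gave this share of replicates with lower AIC for an equally accurate algorithm:

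| b | ρ | n = 6,000 | n = 23,265 |
|---|---|---|---|
| 0 | 0 | 53% | 47% |
| 0.5 | 0 | 85% | 98% |
| 0.5 | 0.5 | 68% | 87% |

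**A bias in the other direction.** Section 4.5.1 has nurses complete the adequacy survey while recording SNCT levels. If 0.2 of SNCT's error enters the rating (b = 0.5, ρ = 0), the signal becomes −0.5T + 0.3e1 + u, variance 0.795. SNCT: 0.675² / (0.795 × 0.875) = 0.66. Algorithm: 0.825² / (0.795 × 1.375) = 0.62. SNCT now fits better.

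**Does a joint model help?** With S, SNCT and algorithm as separate terms and ρ = 0:
- Coefficients are −0.40 and −0.40 at every b, so equal accuracy is recognised.
- Added R² is not: 0.108 (SNCT) against 0.152 (algorithm) at b = 0.5, and 0.050 against 0.133 at b = 1.
- If staffing puts weight 0.5 on SNCT and 0.5 on true need, the coefficients are −0.27 and −0.36 (−0.20 and −0.32 at ρ = 0.5).
- With the shared-rater effect above they are −0.52 and −0.32.

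**The case against.** Four points have force.

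**Shared errors.** Section 4.4.4 aims to reproduce SNCT as closely as possible, so the algorithm will probably inherit part of SNCT's error. That shrinks the gap at equal accuracy (0.51 against 0.53 at ρ = 0.8) but does not remove it. A reader might go further and infer that a less accurate algorithm would match or beat SNCT. With independent errors it can: at 1.5 times SNCT's error variance and b = 0.5, 0.54 against 0.51; at twice the variance and b = 1, a tie at 0.50. At ρ = 0.5 both cases turn in SNCT's favour (0.51 against 0.45; 0.50 against 0.32). Even at ρ = 0, SNCT wins the 1.5-times case at b = 0.3 (0.61 against 0.58). The documents do not support that inference as a general claim.

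**Responsiveness.** Section 2.1 says intermittent assessment limits the ability to match demand in real time. Section 2.2 says timely requirement information is not generally available. Section 2.3 reports 75% of Trusts using professional judgement at shift start. So b is unknown and may be small. It also cannot be inferred that the effect is largest where SNCT is recorded most often, because recording a score is not acting on it.

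**Role of the comparison.** Objective 3 asks about association with outcomes. The plan also has random-intercept and random-slope models and decision curves, and it states no rule for declaring one measure superior or replacing SNCT. That limits the harm. However, the decision curves rest on the same deviations, and the multilevel models do not address how staffing was set.

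**Left to the SAP.** Exact model terms may be. The exposure, comparator and ranking criterion are stated in the protocol, so the point can be raised here.

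**Conclusion.** The point holds in a limited form. In wards and periods where SNCT guided shift staffing, separate-model AIC mixes measurement quality with the effect of SNCT having been used, and no planned analysis separates them. Taken alone, the mechanism favours an equally accurate algorithm. With the assumed variances and b = 0.5, the gap in explained signal runs from 0.13 (0.64 − 0.51) at error correlation 0 to 0.02 (0.53 − 0.51) at 0.8, and it is nil at b = 0.

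A reader might conclude that the Workstream 3 comparison is biased towards the algorithm overall. The documents do not establish that. The shared rater in the micro-survey can reverse the direction, as shown. So can need that raises risk directly and is not adjusted for: one setting with b = 0.5 and smaller error variance (0.25) gave 0.617 for SNCT against 0.576. The supportable conclusion is that the ranking is uninterpretable as accuracy in these wards, not that its sign is known. The calculation assumes that outcomes depend on staffing minus true need and that the two measures are equally accurate.

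**What to change.** 1. Record by Trust, ward and period whether SNCT was used for shift deployment (use, not just recording). Report the algorithm-versus-SNCT comparison separately by that indicator. Base any comparative fit statement mainly on wards and periods where SNCT did not drive shift staffing, noting that establishments there may still reflect SNCT.
2. In deployment-use wards, call separate-model AIC descriptive. Add as a sensitivity analysis one model per outcome with actual care hours, SNCT requirement and algorithm requirement as separate terms. Compare the two requirement coefficients on a common scale (care hours per patient day), not the fit each adds, because added fit still favours the algorithm at equal accuracy. State that the coefficients are only approximately comparable if staffing also follows need through professional judgement, or if the nurse scoring SNCT also rates adequacy.

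**Cost.** Analysis wording, plus one indicator from the Trust contacts who already supply ward context (section 4.4.1). The non-deployment stratum will be smaller: a Trust scoring SNCT only at reviews contributes about 1,200 ward-days against up to 4,653, and the stratum could be nearly empty if most Trusts use SNCT for deployment. In that case no accuracy ranking should be drawn from AIC. The joint coefficients will be imprecise because the two requirements are correlated.

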#### 4.5.1. Data sources

In addition to the **data sources** described in 4.4.1 above, for this workstream we will run a micro-survey of nurses consisting of three questions added to the existing Safer Nursing Care Tool data collection, as well as extracting roster data extracts.

Clinical nurses will answer this tick-box **micro-survey** at the same time that they are already recording the patient acuity/dependency levels, using existing data collection methods, e.g. functionality that is available in the roster systems. We developed this micro-survey for our previous study evaluating the Safer Nursing Care Tool (HS&DR 14/194/21), and it was viable with achieved completion rates of at least 85% per Trust.(13) In this survey we will assess perceived staffing adequacy, which although subjective, has been found to be strongly associated with patient, nurse and organisational outcomes.(51) A strength of these subjective assessments is that they include professional judgement for those aspects of workload that are hard or impossible to measure.(51)

Ethics/ERGO no: 100780; IRAS no: 346148

**Roster data** is required to determine actual staffing, for determination of under/over-staffing compared to each measure of staffing requirements. We will extract both rosters for substantive staff as well as bank/agency rosters if held separately. Where possible we will also source data on the staffing establishment for each ward or estimate these from the roster data.

Patient outcomes will be sourced from **patient administrative systems**. We will consider adverse outcomes identified through diagnosis codes and other administrative data; in our previous study we found that incidents such as deep-vein thrombosis and pressure ulcers identified from diagnosis codes are associated with adverse staffing levels (NIHR 128056 under review). We will not use incident reports because in previous studies), it has been found that incident reports, e.g. from "datix" data, is of poor quality with higher staffed wards tending to record more incidents, possibly due to having more time for reporting.(26, NIHR 128056 under review)

#### Sample sizes

To estimate the sample size for the **perceived staffing adequacy outcomes**, we will assume a similar response rate (85%) as for our previous study. We are aiming to run the micro-survey for at least 9 months including a piloting/training phase of 3 months. We will aim for all eligible wards to complete the micro-survey but will work with Trusts as to what is feasible. In Trusts where SNCT data is only collected during establishment reviews, we will aim for the survey to cover 2 establishment reviews. Based on 20 wards per Trust (average number of wards with micro-survey data from previous study(13)), this would give us between about 1200 (30 day sample x 2 reviews x 20 wards) and 4653 (0.85 completion rate x 9 months x 20 wards) ward days of data per Trust for understanding the relationship between understaffing and perceived staffing adequacy. In total across Trusts this would give us between 6,000-23,265 data points. Based on 626,313 admissions in our previous study corresponding to 5 years' of data from 4 Trusts (NIHR 128056 under review), we estimate that across 5 Trusts in a 9-month period we would have in the region of 100,000 patient admissions for modelling the relationship between understaffing and **patient outcomes**.

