#### 4.2. Scope and selecting research sites

The **scope** of our study is all patients staying on inpatient wards (including admission units) for adult acute somatic (i.e. not mental health) care, as this is the scope of the Safer Nursing Care Tool.

We aim to include a **diverse sample** of hospital wards across a variety of hospital sizes, specialties, and geographical locations. Specifically, we plan to analyse data from at least five NHS hospital Trusts in England (hospitals in other parts of the UK use different staffing tools), starting with our two partner hospital Trusts. To test generalisability, we will recruit at least three further hospitals through groups such as the Shelford Group (who we have preliminary support from) or users of particular Electronic Patient Record systems or roster services such as Oceansblue (who have worked with us on previous projects). We will purposefully over-recruit to allow for drop-off. By collaborating with hospitals serving diverse populations, we aim to reduce the risk of algorithm bias resulting from training on unrepresentative data sets. While it will not be possible to sample to achieve generalisation / representativeness in a statistical sense, selection from willing trusts will be guided by diversity of clinical populations, Trust type (e,g. teaching versus not)

and available data systems. This will increase confidence that algorithms work in diverse settings or identify possible limits of generalisability. We will favour sites who are willing and able to run the micro-survey component.

We have confirmed involvement of **Portsmouth** Hospitals University NHS Trust (where we performed our previous HS&DR studies NIHR 13/114/17 & 128056) and **Imperial** College Healthcare NHS Trust. Portsmouth Trust employs approximately 9,100 whole-time equivalent staff and provides acute services to about 675,000 people across Portsmouth and south-east Hampshire.(35) Imperial Trust employs more than 15,000 staff across five sites, of which three are relevant to our study (Charing Cross, Hammersmith, St Marys).(36) It serves eight London boroughs in the North West London Integrated Care System. Portsmouth has 1103 and Imperial has 1035 general and acute beds.(37)

4.3. **Workstream 1:** Understanding staffing decision support needs and applying user-centred design

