### 6. Project / research timetable

IVIdga		Disseriment	Dissemination								PPIE							Workstream 3							Workstream 2						Workstream 1			Pre-study	Category	
iviagazine article for fluises	Wagazine adicle for purses	Write final report	Conferences	E-newsletter	Engage with user groups	Posters for hospitals	Podcast /blogs/videos	Science and Engineering fair	Workshop with college students	Workshops with patients/families	Recruiting patients to PPI group	Paper on validity of measures of staffing requirements	Regression modelling of staffing adequacy	Regression modelling of patient outcomes	Data linkage and processing	Data extraction 2 (All Trusts)	Micro-survey running	Micro-survey set-up and training and pilot	Paper on estimating staffing requirements from routine data	Testing on other datasets	Fitting algorithms (extensions)	Fitting algorithms - patient-level approach	Fitting algorithms - ward-level approach	Data linkage and processing for algorithms	Data extraction 1 (2 Trusts)	Paper on staffing decision support needs	Workshops (algorithm design considerations)	Thematic analysis of workshop results	Workshops (decision support needs)	Analysing survey results	National survey	Additional Trust recruitment (3+)	Research Fellow recruitment	Ethics, R&D and data governance approvals	What	
												īs							ine data																$\sim$ $01$	-Aug- !-Sep-
			-																																ω 01 4 01	-Oct-
																																			σ 01	-Dec
	1																																		o 01	l-Jan
	-		+																									H							√ 0 1 ∞ 0 1	l-Feb -Mai
t	$^{+}$	t	+									H													r			r								
																																			- 01	-Apr -May
												L																								·uη
	-		-								H														L			H							ω 0.	1-Juj.
+	+										H	H													H		H	H				H			5 0 1	-Aug !-Sep
	t										r	T													Г			r				Г			o 01	!-Oct
																																			~ 01	-Noi
	_		_																						L										∞ 01	-Dec
+	+	+	+				H	H	H	H	H	H						H	H					H	H		H								10 01	l-Jan l-Fel
H	+	+	+				H			H	H	H													H		H		Н						01	-Ma
T	Ť	T																Г											Г						12 07	!-Api
																																			13 01	-Ма
	+									L															L		L	L							14	l-Jur
H	-																					H						H							15 01	1- Jul !-Δ
t			+																			H			H			H							6 01	!-Au t !-Se f

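### The micro-survey sample size applies the assumed 85% completion only to its upper end; the lower end should be 5,100 ward-days, not 6,000, and the upper end depends on an unstated use of pilot data

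*Protocol*

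**What the plan says.** The figures are in the unnumbered Sample sizes section of Workstream 3, between 4.5.1 and 4.5.2 of the protocol. For the perceived staffing adequacy outcomes it states: "we will assume a similar response rate (85%) as for our previous study". Section 4.5.1 gives the source of that rate, saying of the earlier use of the survey that "it was viable with achieved completion rates of at least 85% per Trust".

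The planned duration is "at least 9 months including a piloting/training phase of 3 months". With 20 wards per Trust, the section gives a per-Trust range:

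- **Lower end**, for Trusts that record SNCT data only during establishment reviews: "about 1200 (30 day sample x 2 reviews x 20 wards").
- **Upper end**: "4653 (0.85 completion rate x 9 months x 20 wards) ward days of data per Trust".

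It then scales up: "In total across Trusts this would give us between 6,000-23,265 data points". The timetable in section 6 has a row labelled "Micro-survey set-up and training and pilot", separate from the row for the survey running. Section 10 describes the pilot as a way of finding and dealing with problems. No section says whether responses from the pilot months enter the analysis.

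**The concern.** The two ends of one range rest on different completion assumptions. The section sets 85% for these outcomes, uses it for the larger figure and leaves it out of the smaller one. A lower end that needs complete response from every ward is not a cautious figure.

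The upper end raises a separate question. It credits the piloting and training months with the same 85% as the rest of the survey, without saying that those responses will be used.

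These are the only planning numbers for the perceived-adequacy part of the validation. Section 4.5.3 considers ward-level random-intercept and random-slope models for it, where the number of observations per ward matters. A reader judging feasibility should be able to see what each end assumes.

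**Working it through.** **Inputs** (Workstream 3, Sample sizes, unless noted)

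- Completion: 85%
- Wards per Trust: 20
- Survey length: at least 9 months, of which 3 are piloting and training
- Review-only Trusts: two reviews of 30 days
- Trusts: 5. The same section uses 5 for its admissions estimate, and 23,265 / 4,653 = 5.

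**Step 1. Reproduce the stated figures.**

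- Upper end: 9 months = 365 x 9/12 = 273.75 days. 0.85 x 273.75 x 20 = 4,653.75, truncated to 4,653. 4,653 x 5 = 23,265. Both match.
- Lower end: 30 x 2 x 20 = 1,200. 1,200 x 5 = 6,000. Both match, with no completion factor, so completion is implicitly 100%.

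**Step 2. Apply the stated 85% to the lower end.**

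- Per Trust: 0.85 x 1,200 = 1,020
- Five Trusts: 1,020 x 5 = 5,100
- Change: (6,000 - 5,100) / 6,000 = 15% lower
- Per ward: 60 x 0.85 = 51 survey days instead of 60

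**Step 3. See how far the upper end depends on the pilot months.**

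Excluding 3 months leaves 365 x 6/12 = 182.5 days.

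- Per Trust: 0.85 x 182.5 x 20 = 3,102.5, or 3,102 truncated as in the protocol
- Five Trusts: 3,102 x 5 = 15,510
- Change: (23,265 - 15,510) / 23,265 = 33% lower
- Per ward: 0.85 x 182.5 = about 155 days instead of 0.85 x 273.75 = about 233

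The pilot months (273.75 - 182.5 = 91.25 days) could also be used at a lower completion rate c. The protocol gives no such rate, so the values of c below are assumptions that show the range. Total = (0.85 x 182.5 + c x 91.25) x 20 x 5.

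| Pilot completion c | Total ward-days, five Trusts |
|---|---|
| 0 (pilot not analysed) | about 15,510 |
| 25% | about 17,794 |
| 50% | 20,075 |
| 85% (as the protocol computes it) | about 23,265 |

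The stated total therefore needs full completion from the first day of the pilot.

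**The case against.** **The lower end is only approximate, and other margins could offset the loss.** The range is introduced as approximate. The earlier study achieved 85% or more, section 4.4.2 says reviews last at least 30 days and assumes 40 wards per Trust rather than 20, and all eligible wards are to be approached. Reviews of 36 days at 85% would give 0.85 x 36 x 2 x 20 = 1,224. All this is fair, and it means that realised numbers may fall above or below the range. It does not rescue the calculation: the section chose 85%, 30 days and 20 wards, and then applied the 85% at one end only.

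**The upper end is not wrong as stated.** This objection stands. A reader might infer from the separate timetable rows and the pilot's purpose that pilot responses will be discarded, so that 23,265 is overstated by a third. The protocol does not say so. It counts the pilot as part of the 9 months, the three questions were already used in an earlier study, and 9 months is a minimum. The timetable's month cells cannot be read in the text available, and separate row labels do not show that data are dropped.

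**Two reviews may not fit in the survey.** A reader might argue that reviews held twice a year cannot both be relied on to fall within 9 months, and cut the lower end to a single review. That needs exact six-month spacing together with a hard 9-month limit or exclusion of the pilot. The protocol sets none of these. It states an aim of covering two reviews and leaves the duration open upwards.

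**Not all five Trusts may run the survey.** Section 4.2 says only "We will favour sites who are willing and able to run the micro-survey component". However, the plan is for at least five Trusts with over-recruitment, and the per-Trust figures are already printed, so a reader can rescale.

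**Conclusion.** The lower end is wrong on the protocol's own assumption: 1,200 per Trust and 6,000 in total should be 1,020 and 5,100, which is 15% lower. This rests only on the section's own inputs of 85%, 20 wards, two 30-day reviews and five Trusts.

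The upper end is arithmetically correct but conditional. It stands if all 9 months yield analysable responses at 85%, and becomes about 3,102 per Trust and 15,510 in total if pilot responses are not analysed. The protocol leaves that open. It would go too far to say that both ends are overstated, or to treat the one-third reduction as a correction.

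The consequence is limited. No power target, precision target or decision rule is tied to these numbers, so the fault is an inconsistent planning range and not an invalid design.

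**What to change.** In the Workstream 3 Sample sizes section:

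1. Apply 0.85 to the lower end: 0.85 x 30 x 2 x 20 = 1,020 ward-days per Trust, and 5,100 over five Trusts.
2. For the upper end, either state that pilot-phase responses will be analysed and are assumed to reach 85%, or give the pilot-excluded figure (about 3,102 per Trust, 15,510 in total) beside 4,653 and 23,265.

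The total then runs from 5,100 to 23,265, with 15,510 shown as the alternative upper end if pilot use is left undecided. The cost is one edited paragraph and a slightly less favourable stated range. No planned analysis changes.
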